7.6. Surgery Data

Due to the small overall size of the Surgery Subgroup as described in Section 4.4, efficacy analyses will predominantly be based on assessment of subject data listings.

The following information will be provided in the data listings:

- Dates/times for the various components of the surgical rehabilitation period (hospital admission, surgery, discharge)
- The surgical procedure performed, blood loss, drainage
- Blood products used including details for type of transfusion, date/time administered, and amount given
- Surgeon's/investigator's assessment of hemostatic response to rFVIII Fc
- Dosing during surgery, on the day of surgery, and for the first 14 days post-surgery (Days 1-3, Days 4-14, and Days 1-14)
 - during surgery: number of injections, average dose per injection, and total dose required to maintain hemostasis
 - day of surgery: total dose required to maintain hemostasis
 - post-surgery: total rVIII Fc administered, the total number of injections, and the minimum and maximum intervals of time between injections
- The number of injections required to maintain hemostasis and average daily dose on the day of surgery and for Days 1-3 and Days 4-14 following surgery
- Injections and bleeding episodes during surgery and for the first 14 days following surgery, FVIII levels, reason for injection, nominal dose, hours since the last injection, and if any additional treatment was given to treat the bleed

The following information will be summarized for the FAS:

- Number of injections and mean and total dose per injection required to maintain hemostasis during the major surgical period
- Estimated blood loss during major surgery
- Total rFVIIIFc consumption (IU/kg) per major surgery
- Number of bleeds after surgery per major surgery

In addition, minor surgeries will be summarized and listed where possible in a similar manner for the FAS.

During surgery includes the pre-surgery dose given for the surgery. The day of surgery refers to the calendar day of the surgery and includes the pre-surgery dose given for the surgery, even if it was given on the previous day. Day 1 refers to the day following surgery. The average dose per injection will be determined as the average dose across all injections during the referenced time period. Total dose will be determined as the sum of all doses administered during the referenced time period.

7.6.1. Investigators'/Surgeons' Assessment of Hemostatic Response to Surgery Using the 4-point Bleeding Response Scale

The Investigators'/Surgeons' assessment (using the 4-point surgery response scale detailed in Appendix 2) of the subject's hemostatic response to rFVIIIFc within 24 hours post-surgery will be summarized categorically for all major surgeries for the FAS. Categorically, the number and percentage of surgeries given each rating will be tabulated. Percentages will be based on the number of surgeries for which a response was provided.

The above data will be summarized for both major and minor surgeries in 8HA01EXT.

7.7. Pharmacokinetic Assessments

FVIII activity levels data will be provided in a listing.

8. SAFETY ANALYSIS

Safety data will be summarized for subjects from the parent study or subjects from the parent studies combined along with the overall total. The analysis population for safety analyses is defined in Section 4.3.

Adverse events (AEs) will be summarized for subjects from each parent study and overall for all subjects in study 8HA01EXT, regardless of treatment arm for subjects from studies 997HA301, 997HA307, and 997HA309, age cohort for subjects from study 8HA02PED, and treatment regimen in study 8HA01EXT.

In addition, all data from study 8HA01EXT will be provided in data listings.

8.1. Primary Endpoint

The primary safety endpoint is the occurrence of inhibitor development as determined from the Nijmegen-modified Bethesda assay. A listing of inhibitor test results will be provided.

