Bleeding episodes will be annualized for each subject first, then summarized and tabulated by treatment arm, treatment regimen, or age cohort, as appropriate, in the parent studies. These analyses will also be performed for each type of bleed (spontaneous and traumatic). The number of spontaneous joint bleeding episodes and the consumption of rFVIII Fc will be annualized in a similar fashion and tabulated.

Analysis of surgery endpoints will be performed for subjects who had surgeries during the study, either emergently or electively. Summary statistics of surgery endpoints will be provided for the surgical/rehabilitation period.

Patient-Reported and Health Outcomes

Endpoints for patient-reported outcomes (Haem-A-QoL, Haemo-QoL, Hemo-Sat-Patient, CHO-KLAT Children, CHO-KLAT Proxy, EQ-5D-Y and EQ-5D-3L) will be analyzed in a separate report. These endpoints will be analyzed by summarizing actual values and change from baseline as appropriate.

Summary statistics of health outcome endpoints will be tabulated at each collection timepoint.

Safety

The Safety Population will include all subjects with at least 1 dose of rFVIII Fc. For the analysis of safety, data in 8HA01EXT will be integrated with the parent studies, unless specified otherwise. The incidence of AEs will be tabulated overall, by severity, and by relationship to treatment. In addition, the incidence of AEs will be presented by exposure day (ED) intervals. Findings in clinical lab values will be summarized by descriptive statistics.

The proportion of subjects with inhibitors during rFVIII Fc administration will be provided with the exact (Clopper-Pearson) 2-sided, 95% confidence interval.

Interim Analyses:

Interim analyses will be conducted during the study, as needed. Analyses will be descriptive in nature. No formal comparisons are planned and no hypotheses will be formally tested.

Due to the open-label nature of this study, personnel involved in conducting the interim analyses will have access to treatment assignments.

Sample Size Determination:

This is an extension study. Sample size is based on sample sizes of Studies 997HA301 (N=144) and 8HA02PED (N=50), and may be increased based upon subject participation in other rFVIII Fc studies.

Study Stopping Rules:

The Sponsor may terminate this study at any time, after informing Investigators.

Study stopping is required if any of the following occur:

CONFIDENTIAL

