16.7.2. Methods of Analysis

The proportion of subjects with inhibitors during rFVIII Fc administration will be provided with the exact (Clopper-Pearson) 2-sided, 95% confidence interval. Any subject with an inhibitor following the initial rFVIII Fc administration will be counted in the numerator; however, only subjects who have completed at least 50 EDs and 100 EDs from their initial rFVIII Fc administration will be included in the denominator. Unless all subjects complete at least 50 EDs, the proportion of subjects with inhibitors will also be calculated using all subjects, regardless of the amount of exposure to rFVIII Fc, in the denominator.

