5. DATA HANDLING

This study is being conducted under the sponsorship of Biogen. Data management is being performed under contract with Quintiles in collaboration with Bioverativ. Statistical analysis is being performed by Bioverativ, using SAS® version 9.3 or higher and, where appropriate, additional validated software. This statistical analysis plan (SAP) is based on protocol Version 3, dated 26 August 2013 and will detail analyses to be performed and summaries to be produced for the final Clinical Study Report (CSR).

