8.3.2. Inhibitor Development

Inhibitor results of the Nijmegen-modified Bethesda Assay from the central lab will be listed. Results from blood samples collected during surgical/rehabilitation periods for the purpose of determining the presence of an inhibitor will be included.

A positive inhibitor occurs where a subject has a value ≥ 0.6 Bethesda Units (BU/mL) confirmed on re-testing between 2 and 4 weeks later. Both tests must be performed by the central laboratory.

A “low” titer inhibitor occurs where a subject has a value between 0.6 and <5.0 Bethesda Units (BU/mL) confirmed on re-testing between 2 and 4 weeks later.

A “high” titer inhibitor occurs where a subject has a value ≥ 5.0 Bethesda Units (BU/mL) confirmed on re-testing within 2 to 4 weeks.

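### The SAP plans only a listing as the dedicated analysis of the sole primary endpoint, inhibitor development, where Protocol 16.7.2 requires proportions with exact 95% confidence intervals by exposure-day denominator

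*SAP*

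**What the plan says.** Protocol 6.2.1 and SAP 2.2.1 both name inhibitor development as the only primary endpoint.

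**Protocol.** The synopsis states: "The proportion of subjects with inhibitors during rFVIII Fc administration will be provided with the exact (Clopper-Pearson) 2-sided, 95% confidence interval". Section 16.7.2 repeats this and defines the ratio. Numerator: "Any subject with an inhibitor following the initial rFVIII Fc administration will be counted in the numerator". Denominator: "only subjects who have completed at least 50 EDs and 100 EDs from their initial rFVIII Fc administration will be included in the denominator". If anyone falls short of 50 EDs, the proportion "will also be calculated using all subjects, regardless of the amount of exposure to rFVIII Fc, in the denominator". Section 16.6.2 separately asks for total EDs, including an overall summary that combines the parent studies with 8HA01EXT.

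**SAP.** Section 5 says that the SAP "is based on protocol Version 3, dated 26 August 2013", so it was written for the same protocol. Section 8.1 gives one output for the primary endpoint: "A listing of inhibitor test results will be provided". Section 8.3.2 defines positive, low-titer and high-titer inhibitors and says: "Inhibitor results of the Nijmegen-modified Bethesda Assay from the central lab will be listed". The list of listings includes inhibitor results, but the list of tables has no inhibitor table. Section 1 limits the analysis to 8HA01EXT data. Section 7.3.2 counts EDs from the start of the first regimen in the extension. No inhibitor proportion, ED denominator or confidence interval appears in the supplied SAP, and no reason is given for departing from 16.7.2.

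**The concern.** A listing shows individual assay results. It does not state a rate or its precision. With few or no cases, the upper confidence limit is the main quantitative statement that a single-arm inhibitor study can make, and that is what drops out.

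The ED denominators matter too. The protocol defines risk against cumulative exposure from the first dose, and SAP 3.1 keeps subjects first dosed under 12 years in follow-up to 100 EDs across parent and extension studies. If EDs are counted only within the extension, the report cannot fully say who reached that exposure, and the combined ED summary of Protocol 16.6.2 is missing as well.

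**Working it through.** **1. Planned sizes reproduce.** Protocol 16.10: 144 + 50 = 194. SAP 3.3.1: 144 + 50 + 12 + 8 = 214. The study is descriptive, so there is no power calculation to check.

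**2. What the omitted interval would say.** Exact (Clopper-Pearson) limits for x cases in n subjects:
- lower = 2.5th percentile of Beta(x, n − x + 1), or 0 if x = 0
- upper = 97.5th percentile of Beta(x + 1, n − x), which for x = 0 equals 1 − 0.025^(1/n)

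The case counts are assumptions. So are n = 150 and n = 100, which stand for denominators reduced by an ED threshold.

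| n | Source of n | Upper limit, 0 cases | 1 case: estimate (95% CI) |
|---|---|---|---|
| 214 | SAP plan | 1.71% | 0.47% (0.01 to 2.58) |
| 194 | Protocol plan | 1.88% | 0.52% (0.01 to 2.84) |
| 150 | assumed | 2.43% | 0.67% (0.02 to 3.66) |
| 100 | assumed | 3.62% | 1.00% (0.03 to 5.45) |
| 50 | 8HA02PED plan | 7.11% | 2.00% (0.05 to 10.65) |

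Check: 1 − 0.025^(1/214) = 0.01709, and the probability of no cases at that risk is 0.025.

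**3. What extension-only EDs can and cannot show.** Protocol 5.1.3 gives at least 50 EDs as the 8HA02PED target. A child with 50 parent-study EDs and 50 to 99 extension EDs has 100 to 149 in total. He belongs in the 100-ED denominator but falls in the SAP 7.3.2 band of 50 to under 100. Conversely, anyone with 100 or more extension EDs qualifies whatever his earlier exposure. Dosing every 3 to 5 days reaches that in about 100 × 3 = 300 to 100 × 5 = 500 days, and weekly dosing in about 100 × 7 = 700 days. Participation may last up to 4 years but can end sooner if the product is marketed locally. The planned outputs therefore give a partial count, and the documents do not allow the shortfall to be estimated.

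**4. What the serious adverse event table supplies.** Protocol 15.2.3 makes every inhibitor a reportable serious event, and SAP 8.2.6 tabulates treatment-emergent serious events over the Safety Analysis Set. A crude incidence by preferred term may therefore appear. It has no interval and no ED denominator. SAP 8.2.1 keeps events in major surgical/rehabilitation periods out of every adverse event table except the overall summary. SAP 8.2 excepts only events with onset on the day the period starts or the day of surgery. Protocol 10.1.3 schedules inhibitor tests 1 to 2 weeks after major surgery and at the last post-operative visit, so a case could first be found inside the omitted window.

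**5. A defect in 16.7.2 that should not be copied.** Any inhibitor case enters the numerator, but only subjects past the ED threshold enter the denominator. Suppose one case arises before 50 EDs and 49 other subjects reach 50. The literal ratio is 1/49 = 2.04%, with the case absent from the denominator. Including him gives 1/50 = 2.00%. The difference is small, but only the second ratio is a binomial proportion to which Clopper-Pearson applies.

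**The case against.** The strongest reply is that nothing is lost. The protocol already fixes the estimator and interval, and SAP silence does not repeal them. SAP 8 says in general that safety data will be summarized, table titles are only suggested, and the shells and some SAP pages are not available here. Inhibitors will also appear as serious events.

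Part of this stands. The point is limited to the supplied text, and a crude incidence may well be tabulated. But SAP 5 says that the SAP details the analyses for the final report, and its section on the primary endpoint names a listing. The general sentence supplies neither an interval nor an ED denominator.

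A reader might infer three stronger things that the documents do not support:
- **That the 50-ED and 100-ED estimates are beyond recovery.** They are not fully available from the planned outputs. Extension EDs already identify some qualifying subjects, and existing parent-study data can supply the rest. An all-subject interval could be worked out from the listing and the size of the Safety Analysis Set.
- **That restricting safety tables to 8HA01EXT is itself a breach.** Protocol 16 and 16.6.2 qualify general data integration. The EDs from first dose in 16.7.2 and the combined ED summary in 16.6.2 carry no such qualifier.
- **That inhibitor results from surgical periods disappear.** SAP 8.3.2 keeps those samples in the listing. They may be absent only from the serious adverse event table.

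**Conclusion.** The mismatch is real and should be corrected before the final analysis. In the supplied text, the SAP's dedicated analysis of its sole primary endpoint is a listing. The protocol version on which the SAP is based requires proportions with exact 95% intervals. If the SAP is followed, no interval is planned, there is no estimate at 50 or 100 cumulative EDs, and the combined ED summary is missing.

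The sizes in the table are illustrations that assume planned enrollment and zero or one case; they predict nothing. The conclusion also rests on reading the 50-ED and 100-ED wording of 16.7.2 as two separate denominators. That is the better reading, because the all-subject calculation is triggered by the 50-ED threshold alone. The documents do not show whether the omission was deliberate.

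**What to change.** 1. Add to SAP 8.1 and the table list an inhibitor table with number, proportion and exact Clopper-Pearson two-sided 95% interval for the 50-ED, 100-ED and all-subject denominators.
2. Count EDs from first rFVIIIFc by merging existing parent-study data. State the rule at the parent/extension boundary and across gaps, because SAP 5.1.1 often sets extension Study Day 1 at the last parent-study day and SAP 7.3.2 restarts the ED window in the extension.
3. Include every subject with an inhibitor in the denominator even if he has not reached the ED threshold, and record this as a clarification of 16.7.2.
4. State which set defines all subjects. Protocol 16.6.1 requires at least one dose of rFVIIIFc with no restriction to the extension, whereas SAP 4.3 requires a dose in 8HA01EXT. If the SAP set is used, document it as a narrowing of the protocol set.
5. Add the combined parent-plus-extension ED summary of Protocol 16.6.2.
6. If the sponsor intends to drop the 16.7.2 analysis, say so in the SAP and give the reason.

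Cost: one table, one ED summary, and a data merge with boundary rules that the SAP does not currently plan. No new data collection.

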8.2. Adverse Events

AEs will be classified using the Medical Dictionary for Regulatory Activities (MedDRA) system organ classes and preferred terms. MedDRA version 15.0 will be used throughout the study. All AEs will be listed.

In general, AEs will be analyzed based on *incidence*, defined as the proportion of subjects who had at least one occurrence of an event out of the number of subjects in the Safety Analysis Set.

All adverse event listings will include the onset and resolution study days relative to 8HA01EXT Study Day 1. AEs that are emergent during a major surgical/rehabilitation period, AEs that are emergent on the day of surgery and AEs that occur during the gap of greater than 7 or 4 days will be flagged. In addition, a separate listing will be provided for AEs that are emergent during a major surgical/rehabilitation period.

AEs occurring during a major surgical/rehabilitation period with an onset date on the day the surgical/rehabilitation period starts or on the day of the surgery will be included in the summaries of the study AEs but excluded from the summaries or listings of AEs occurring during a major surgical/rehabilitation period. Consideration is given to AEs with an onset date at the start of the surgical/rehabilitation period in the event the pre-surgical dose was administered the day before the surgery.

Events of overdose will not be included in the AE summary tables unless they are reported as adverse events.

The algorithm for the determination of AEs that are emergent during a major surgical/rehabilitation period, AEs with an onset date on the day of the surgical/rehabilitation period starts or on the day of the surgery, and AEs that are emergent during a treatment regimen period when an onset date is partially or completely missing is described below.

- If the onset date of an adverse event is present, then the date of onset will be compared with the start/stop dates of the major surgical/rehabilitation period and treatment regimen period to determine whether the adverse event is during a major surgical/rehabilitation

period, on the day of the surgical/rehabilitation period starts or on the day of the surgery, or during a treatment regimen period. If the onset of the adverse event is on the day of the treatment regimen change, then it will be attributed to the previous treatment regimen.

- If the onset day of an adverse event is missing and the onset month and year of the AE are completely within a major surgical/rehabilitation period or a treatment regimen period, then the AE will be attributed to that major surgical/rehabilitation period or that treatment regimen period. For example, the onset of an AE is recorded as 2013-03. A major surgical/rehabilitation period for that subject needs to cover at least from 00:01 on the later date of 2013-03-01 and 8HA01EXT Study Day 1 to 23:59 on the earlier date of 2013-03-31 and the end of his safety period for that AE to be attributed to that major surgical/rehabilitation period. Similarly, if the start and stop time of a treatment regimen do not completely cover the possible range of the onset of AE, then the treatment regimen for that AE will be set to unknown. Regardless of the above, the AE will not be attributed to the day the major surgical/rehabilitation period starts or the day of the major surgery because the exact date is missing.
- If the onset day and month of an adverse event are missing and the onset year of the AE is completely within a major surgical/rehabilitation period or a treatment regimen period, then the AE will be attributed to that major surgical/rehabilitation period or that treatment regimen period. For example, the onset of an AE is recorded as 2013. A major surgical/rehabilitation period for that subject needs to cover at least from 00:01 on the later date of 2013-01-01 and 8HA01EXT Study Day 1 to 23:59 on the earlier date of 2013-12-31 and the end of his safety period for that AE to be attributed to that major surgical/rehabilitation period. Similarly, if the start and stop time of a treatment regimen do not completely cover the possible range of the onset of AE, then the treatment regimen for that AE will be set to unknown. Regardless of the above, the AE will not be attributed to the day the major surgical/rehabilitation period starts or the day of the major surgery because the exact date is missing.
- If the AE onset date is completely missing, the AE will be considered to be outside any major surgical/rehabilitation period and the treatment regimen for that AE will be set to unknown.

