5.3.3. Surgical/Rehabilitation Period

The broadest span of time for the surgical/rehabilitation period in study 8HA01EXT is from the first dose of rFVIIIIFc in study 8HA01EXT given for the surgery (i.e., the pre-surgery dose) up to 1 minute before the first regular prophylactic dose after the last day of postoperative care/rehabilitation for subjects on prophylactic regimens and up to 23:59 on the last day of the surgical/rehabilitation period for subjects on the episodic regimen. If dose(s) labeled for a surgical reason which do not correspond to a surgery will be re-classified as 'OTHER' and will not be used in the determination of the surgical/rehabilitation period. Since not all subjects will have these events, specific considerations for the start and end of the surgical/rehabilitation period are as follows:

Start of the surgical/rehabilitation period:

- Date/time of the first pre-surgical dose. In general, if an injection for a pre-surgical dose is recorded in the eCRF, the reason for the injection should be labeled as "prophylaxis pre-operative". If an injection for pre-surgical dose is recorded in the EPD, the reason will be labeled as "surgical prophylaxis". If the date/time of surgery is complete, a pre-surgery dose is any dose labeled for a surgical reason on the day of, or the day before surgery, which is prior to the start date/time of the surgery. If the time of surgery is missing or 00:00 (as sometime occurs for minor surgeries), only injections labeled as "prophylaxis pre-operative" on the day of surgery should be taken as a pre-surgical dose along with any other doses labeled for a surgical reason on the day before surgery. If there is more than one pre-surgical dose, then the first one should be selected (a pre-surgical dose can be administered the day before the surgery).
- If there is no pre-surgical dose but there was a prophylaxis dose or dose given for "OTHER" reason prior to the surgery on the day of or the day before surgery, the last of these doses should be selected.
- If there is no pre-surgical dose or a prophylaxis dose prior to the surgery on the day of or the day before surgery then select the start date/time of the surgery. If the time was not recorded or recorded as 00:00 then select the date and impute 00:01 for the time.

End of the surgical/rehabilitation period:

If the treatment regimen after the surgical/rehabilitation period is a prophylactic regimen, then the end of the surgical/rehabilitation period is

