Within the total surgical/rehabilitation period, the time is divided into:

- Intraoperative period: from the date/time of the pre-surgery rFVIIIIFc dose to the date/time of the end of surgery
- Postoperative care period: from the date and time plus 1 minute following the end of surgery to the last dose of rFVIIIIFc given for the surgery, including doses given to prevent bleeding during the postoperative period

- Postoperative rehabilitation period: from the date following the last day of postoperative care to the end of the surgical period as described above

The surgical/rehabilitation period will be determined in the same manner for both major and minor surgeries.

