8.2.1. Overall Summary of Treatment-emergent Adverse Events

An overall summary of treatment-emergent adverse events (TEAEs) will be provided which tabulates the number and percentage of subjects who experienced a TEAE, related TEAE, treatment-emergent SAE, or treatment-emergent related SAE; the number and percentage of subjects who discontinued treatment or withdrew from the study due to an AE; and the number and percentage of subjects who died. This table will also be presented by subgroup based upon contemporaneous entry compliance of $\geq 80\%$, as described in Section 6.5.5.3.

AEs that occurred during major surgical/rehabilitation periods will be included in the overall summary of AEs (in the surgery subgroup column) but not in any of the other AE summary tables.

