Listing of the number of bleeding episodes during the efficacy period
Listing of physician's assessment of the subject's global response to his treatment regimen
Listing of major surgery information – hospitalization data

Listing of major surgery information – blood loss
Listing of major surgery information – dosing during and for the first 14 days post-surgery
Listing of major surgery information – transfusions and surgeon’s assessment of hemostatic response to rFVIIIc
Listing of minor surgery information – hospitalization data
Listing of minor surgery information – blood loss
Listing of minor surgery information – dosing during and on the day of surgery
Listing of minor surgery information – transfusions and surgeon’s assessment of hemostatic response to rFVIIIc
Listing of injections and bleeding episodes during and for the first 14 days following major surgery
Listing of FVIII activity levels
Listing of adverse events
Listing of adverse events reported during major surgical/rehabilitation periods
Listing of serious adverse events
Listing of adverse events leading to discontinuation of treatment and/or the study
Listing of adverse events reported in study 8HA01EXT that started before 8HA01EXT Study Day 1 but were not reported in the parent study
Listing of deaths
Listing of laboratory normal ranges
Listing of laboratory values: Hematology (WBC and differential, absolute count)
Listing of laboratory values: Hematology (WBC and differential [%])
Listing of laboratory values: Hematology (red blood cell parameters and platelet count)
Listing of abnormal laboratory values based on the normal range: Hematology
Listing of abnormal laboratory values based on potentially clinically significant abnormalities: Hematology
Listing of laboratory values: Blood Chemistry (liver and renal parameters)
Listing of laboratory values: Blood Chemistry (electrolytes and other parameters)
Listing of abnormal laboratory values based on the normal range: Blood Chemistry
Listing of abnormal laboratory values based on potentially clinically significant abnormalities: Blood Chemistry
Listing of laboratory values: Inhibitor results
Listing of laboratory values: Anti-rFVIIIc antibodies
Listing of vital sign measurements
Listing of abnormal findings from physical examination
Listing of CHO-KLAT questionnaire (Part 1 of 4)
Listing of CHO-KLAT questionnaire (Part 2 of 4)
Listing of CHO-KLAT questionnaire (Part 3 of 4)
Listing of CHO-KLAT questionnaire (Part 4 of 4)

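### The surgical-period AE outputs leave out AEs starting on the day of surgery or the day the period starts, and SAP 8.2 and 8.2.1 disagree on where those AEs are counted

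*SAP*

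**What the plan says.** **Exclusion rule (SAP 8.2).** The rule applies to AEs in a major surgical/rehabilitation period "with an onset date on the day the surgical/rehabilitation period starts or on the day of the surgery". These AEs "will be included in the summaries of the study AEs" "but excluded from the summaries or listings of AEs occurring during a major surgical/rehabilitation period". The only explanation given is that the pre-surgical dose may have been administered on the day before surgery.

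**Period definition (SAP 5.3.3).** The period begins at "Date/time of the first pre-surgical dose". If there is none, it begins at the last prophylaxis dose (or dose given for another reason) before surgery on the same day or the day before. Failing that, it begins at the start of surgery. The subdivision reads "Intraoperative period: from the date/time of the pre-surgery" dose, ending when surgery ends.

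**Affected outputs.** One is the surgery subgroup column of the overall TEAE summary. SAP 8.2.1 states: "AEs that occurred during major surgical/rehabilitation periods will be included in the overall summary of AEs (in the surgery subgroup column"), and adds that no other AE summary table will contain them. The other is the separate listing that 8.2 promises, titled in the List of Listings as "Listing of adverse events reported during major surgical/rehabilitation periods".

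**What is kept.** All AEs are listed. SAP 8.2 also asks for a flag on "AEs that are emergent on the day of surgery" in the AE listings.

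**The concern.** A reader who wants to know which AEs arose around major surgery will go to the surgery subgroup column and the surgical AE listing. If the rule removes the operation itself from both, they describe mainly the post-operative course from the next day onward, under a label that promises the whole period. A reaction to the pre-operative dose, or a thrombotic event on the table, would be missing from them. Protocol 15.2.3 requires vascular thrombotic events and Grade 2 or greater allergic reactions to be reported as SAEs.

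The stated reason does not reach far enough. It explains why the first day of the period needs thought when the dose is given the evening before. It does not explain why AEs starting on the day of surgery should leave the surgical outputs.

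The instructions in 8.2 and 8.2.1 also differ, so two programmers could produce different tables from the same data.

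**Working it through.** The plan gives no figure to reproduce, so the check is one of date logic followed by a comparison of the two sections.

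**Step 1: days covered.** Call the calendar day on which surgery starts day 0. From SAP 5.3.3, the pre-surgery dose is on day −1 or day 0, and the intra-operative period runs from the dose to the end of surgery. From SAP 8.2, the excluded onset days are the day of the dose and day 0. If surgery ends by 24:00 on day 0, the intra-operative period lies wholly within those days and nothing of it remains. The fallback start points fall on the same two days.

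**Step 2: enumeration.** Start times and durations below are assumptions; the documents give none.

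| Assumed grid | Combinations | With intra-operative time outside the excluded days |
|---|---|---|
| Any start time, 0.5 to 12 h, 30-minute steps | 82,368 | 24,196, all with surgery ending after midnight |
| Start 07:00 to 15:45, 0.5 to 8 h, 15-minute steps | 157,914 | 0 |

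The second result is forced: the latest possible end is 15:45 + 8 h = 23:45. The grids test the logic and are not a realistic case mix.

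**Step 3: missing onset day.** SAP 8.2 never assigns an AE with a missing onset day to the start day or the day of surgery. It can therefore reach the surgical outputs if its whole possible onset range lies in the period. This is a narrow route, but it means that a vaguely dated AE can stay where a precisely dated one is removed.

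**Step 4: 8.2 against 8.2.1** for an AE dated to the start day or the day of surgery:

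| Output | SAP 8.2 | SAP 8.2.1, read literally |
|---|---|---|
| Surgery subgroup column | No | Yes |
| Other study AE summary tables | Yes | No |

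The sections give opposite answers in both rows. If the more specific rule prevails, 8.2 governs and the conclusion of Step 1 stands.

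**Step 5: size.** With n operated subjects, a of them with any AE in the period and b with AEs only on excluded days, the column shows (a − b)/n instead of a/n. Purely as an assumed example, n = 20, a = 8 and b = 3 gives 5/20 = 25% instead of 8/20 = 40%. With n and a unchanged, b could be anything from 0 (40%, no effect) to 8 (0%).

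**The case against.** **The AEs are moved, and arguably gain visibility.** This stands as a limit on the point. The surgery column holds only subject counts (any TEAE, related, serious, leading to discontinuation, death). The study tables in SAP 8.2.2 to 8.2.6 break AEs down by system organ class, preferred term, severity, relationship and seriousness. A reader might infer that intra-operative AEs disappear from the report. The documents do not support that, since these AEs remain in the study summaries and the full listing. Even so, a flag in a general listing does not change what the surgical outputs show.

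**Peri-operative safety is covered elsewhere.** A reader might also infer that the two AE outputs are the only peri-operative safety information. They are not. SAP 7.6 and 7.6.1 cover blood loss, transfusion, dosing, bleeds and hemostatic response. SAP 8.3.2 and 8.3.3 include inhibitor and antibody samples from surgical periods. Nor is surgical bleeding a good example of a missing AE: Protocol 15.1.2 does not treat bleeds as AEs unless serious, and Protocol 10.1.3 does not have bleeding caused directly by surgery reported.

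**Simple inclusion would distort the column.** This is the strongest objection, and it stands. Protocol 10.1.3 makes every major surgery an SAE. If those SAEs are dated to the operation, including that day would push the column's TEAE and SAE rates towards 100%. SAP 3.2.2 adds that before Amendment 2 only major surgeries that were not prescheduled were SAEs, so the column would mix two reporting rules. The SAP does not give this as its reason for the rule, but the remedy has to deal with it.

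**Same-day events cannot be ordered.** SAP 8.2 compares onset dates, and Protocol 15.5 asks for dates; neither shows that onset times are collected. This also stands. It argues for flagging these AEs, and it rules out a remedy that depends on recorded times.

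**Conclusion.** The point holds as a matter of labelling and consistency. Under SAP 8.2 and 5.3.3 together, a fully dated intra-operative AE can appear in the surgical-period AE outputs only if surgery crosses midnight and the AE starts after midnight. This assumes that the 8.2 rule prevails over 8.2.1 and that the day of surgery means the calendar day on which it starts. Separately, 8.2 and 8.2.1 contradict each other and need to be reconciled whichever display is chosen.

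The numerical effect is unknown. The 25% against 40% example in the working is an illustration and should not be quoted as an estimate. The study is descriptive, and the primary endpoint of inhibitor development is unaffected. The rule is worth correcting because long-term safety is the primary objective and the change is cheap.

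**What to change.** 1. In SAP 8.2, replace the exclusion. AEs with onset on the period's start day or on the day of surgery should enter both the surgical AE listing and the surgery subgroup column, with a flag. The flag should also mark the start day when that is the day before surgery, because 8.2 names a specific flag only for the day of surgery.
2. In the surgery subgroup column, put SAEs that only record the major surgery itself on a separate line, or give the rates with and without them. State that the SAE reporting rule for surgeries changed at Amendment 2.
3. Keep these AEs in the study AE tables, and amend SAP 8.2.1 to say that start-day and day-of-surgery AEs are counted in both places.
4. Do not make inclusion depend on onset times unless these are confirmed to be collected.

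**Cost.** A few SAP sentences, one changed filter, one flag and one extra table line, plus a review to identify the SAEs that only record the operation. The downside is that some AEs that began before the dose on the same day will appear, flagged, in the surgical outputs. Footnotes should say that these AEs are counted in two places and that the order of same-day events is not known.
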